6.3.2 Hypersensitivity Reactions

Hypersensitivity reactions rarely occur. If they do occur, minor symptoms such as flushing, skin reactions, dyspnea, lower back pain, hypotension, or tachycardia may require no intervention; however, severe reactions, such as hypotension requiring treatment, dyspnea requiring bronchodilators, angioedema, or generalized urticaria require immediate discontinuation of study drug administration and aggressive symptomatic therapy. Patients who experience a severe hypersensitivity reaction to DSF should discontinue DSF immediately and not be re-challenged.

7.0 REGULATORY AND REPORTING REQUIREMENTS

7.1 Adverse Events (AEs)

Definition: any unfavorable medical occurrence including any abnormal sign, symptom, or disease.

Grading: the descriptions and grading scales found in the revised NCI Common Terminology Criteria for Adverse Events (CTCAE) version 4.0 (2009) will be utilized for all toxicity reporting. A copy of the CTCAE version 4.0 can be downloaded from the CTEP website:

http://ctep.cancer.gov/protocolDevelopment/electronic_applications/ctc.htm.

Attribution (relatedness), Expectedness, and Seriousness: the definitions for the terms listed that should be used are those provided by the Department of Health and Human Services' Office for Human Research Protections (OHRP). A copy of this guidance can be found on OHRP's website: <http://www.hhs.gov/ohrp/policy/advevntguid.htm>

7.2 Unanticipated Problems

Definition:

- unexpected (in terms of nature, severity, or frequency) given (a) the research procedures that are described in the protocol-related documents, such as the IRB-approved research protocol and informed consent document; and (b) the characteristics of the subject population being studied;
- related or possibly related to participation in the research (in this guidance document, possibly related means there is a reasonable possibility that the incident, experience, or outcome may have been caused by the procedures involved in the research); and
- any factual suggestion that the research places subjects or others at a greater risk of harm (including physical, psychological, economic, or social harm) than was previously known or recognized.

7.3 Noncompliance

Definition: failure to follow any applicable regulation or institutional policies that govern human subjects' research or failure to follow the determinations of the IRB. Noncompliance may occur due to lack of knowledge or due to deliberate choice to ignore regulations, institutional policies, or determinations of the IRB.

7.4 Serious Noncompliance

Definition: noncompliance that materially increases risks, that results in substantial harm to subjects or others, or that materially compromises the rights or welfare of participants.

7.5 Protocol Exceptions

Definition: A planned deviation from the approved protocol that are under the research team's control. Exceptions apply only to a single participant or a singular situation.

Protocol exceptions are not expected or encouraged, and should be discussed first with the Study Sponsor.

7.6 Reporting to the Institutional IRB

The PI is required to promptly notify the IRB of the following events:

- Any unanticipated problems involving risks to participants or others or that impact participants or the conduct of the study.
- Noncompliance with federal regulations or the requirements or determinations of the IRB.
- Receipt of new information that may impact the willingness of participants to participate or continue participation in the research study.

These events must be reported to the IRB within **10 working days** of the occurrence of the event or notification to the PI of the event. The death of a research participant that qualifies as a reportable event should be reported within **1 working day** of the occurrence of the event or notification to the PI of the event.

7.7 Reporting to the FDA

The conduct of the study will comply with all FDA safety reporting requirements. It is the responsibility of the investigator and Aurora ANII Clinical Research team to report any unanticipated problem to the FDA as follows:

- Report any unexpected fatal or life-threatening adverse experiences associated with use of the drug (i.e., there is a reasonable possibility that the experience may have been caused by the drug) by telephone or fax no later than **7 calendar days** after initial receipt of the information. A life-threatening adverse experience is defined as any adverse drug experience that places the subject (in the view of the investigator) at immediate risk of death from the reaction as it occurred, i.e., it does not include a reaction that, had it occurred in a more severe form, might have caused death.
- Report any serious, unexpected adverse experiences, as well as results from animal studies that suggest significant clinical risk within **15 calendar days** after initial receipt of this information. A serious adverse drug experience is defined as any adverse drug experience occurring at any dose that results in any of the following outcomes:
 - Death
 - Is life-threatening
 - Inpatient hospitalization or prolongation of existing hospitalization
 - A persistent or significant disability/incapacity (i.e., a substantial disruption of a person's ability to conduct normal life functions)
 - A congenital anomaly/birth defect
 - Any other experience which, based upon appropriate medical judgment, may jeopardize the subject and may require medical or surgical intervention to prevent one of the outcomes listed above

An unexpected adverse drug experience is defined as any adverse drug experience, the specificity or severity of which is not consistent with the current investigator brochure (or risk information, if an IB is not required or available).

All MedWatch (Form FDA 3500A) forms will be sent by ANII Clinical Research Team to the FDA at the following address or by fax:

Food and Drug Administration
Center for Drug Evaluation and Research
Division of Oncology Drug Products
[name]
[name]
FAX: [name]

7.8 Timeframe for Reporting Required Events

Reportable adverse events will be tracked for 30 days after the last dose of DSF-Cu.

8.0 PHARMACEUTICAL INFORMATION

8.1 Disulfiram

8.1.1 Disulfiram Description

DSF is an alcohol antagonist drug approved by the FDA for the treatment of alcoholism. Its powder is white, odorless, and almost tasteless. It is soluble in water to the extent of about 20mg in 100mL, and in alcohol to the extent of about 3.8 g in 100 mL.

Molecular formula: C₁₀H₂₀N₂S₄

Chemical name: bis(diethylthiocarbamoyl) disulfide.

Molecular weight: 296.54.

8.1.2 Clinical Pharmacology

DSF is mostly known as an irreversible inhibitor of aldehyde dehydrogenase, which affects alcohol metabolism and causes accumulation of acetaldehyde. However, increasing preclinical studies have shown that DSF is also a proteasome inhibitor, specifically the chymotrypsin-like activity.

Glioblastoma cells and its stem-like subpopulation (also referred to as CSC) may be more susceptible to the effect of proteasome inhibition than normal brain cells. DSF is an effective MGMT inhibitor. DSF is very lipophilic and readily crosses the blood-brain barrier.

8.1.3 Supplier

ANII Clinical Research Team together with the Aurora Saint Luke's Pharmacy Committee will decide upon a US unique manufacturer / supplier of DSF. Aurora Pharmacy Committee will ensure that for the purposes of the study that Aurora Saint Luke's dispensing pharmacy will ensure cutting DSF 250 mg tabs into halves.

8.1.4 Dosage Form

DSF will be supplied in roughly 125 mg per dose (one half of 250 mg tab).

8.1.5 Storage and Stability

DSF is dispensed in a tight, light-resistant container. It should be stored at controlled room temperature (20° to 25°C or 68° to 77°F) in its original container to protect from bright light.

8.1.6 Disulfiram Administration

DSF is taken by mouth two times daily. It should be taken with meals to improve absorption. It should not be taken within one hour of temozolomide. Patients should not have consumed any alcohol at least 12 hours prior to the first dose. In the rare event of a severe hypersensitivity reaction, discontinue DSF immediately.

8.1.7 Supplier

DSF will be dispensed via the Aurora Saint Luke's Pharmacies and provided by US manufacturer of choice which will be designated following review by the ANII Research Team and by the Aurora Pharmacy Committee

8.1.8 Copper Gluconate Description

Cu gluconate is a dietary food supplement generally recognized as safe (GRAS) under §21CFR184.1260. Cu is an important nutrient in the human body and plays an essential role by participating in numerous metabolic reactions in the body (Lecyk 1980; Stern et al. 2007). Exposure to Cu usually occurs from consumption of food and drinking water. Several studies have concluded that chronic dietary intakes of Cu less than 10 mg/day pose no significant health risk

8.1.9 Dosage Form

Copper gluconate is supplied as 2 mg capsules/tablets.

8.1.10 Storage and Stability

Copper gluconate is dispensed in a tight, light-resistant container. It should be stored at controlled room temperature (20° to 25°C or 68° to 77°F) in its original container to protect from bright light.

8.1.11 Copper Gluconate Administration

Copper gluconate is taken by mouth two times daily. It should be taken with meals and at the same time with DSF.

8.1.12 Supplier

A sufficient supply of Copper Gluconate will be purchased by Aurora Research Institute and will be provided to subjects participating in this study at no cost to the subject.

9.0 STUDY CALENDAR

Screening/baseline evaluations are to be conducted within 4 weeks (+/- 7 days) prior to start of protocol therapy. Scans will be performed prior to the start of the protocol therapy. Each treatment cycle is 28 days.

	Screening / Baseline	Weekly during radiation treatment	Start of Fourth Week of radiation therapy	Day 1 of Each Cycle (+/- 7 days)	End of Every Even-Numbered Cycle	Day 1 of Cycle 1 (+/- 7 days)	Day 1 of Cycle 4 (+/- 7 days)	End of Treatment	Follow-Up ¹
Informed consent	X								
H&P incl. neurologic exam, ECOG	X			X				X	
Evaluation of corticosteroid usage	X		X	X					
CBC	X	X		X					
CMP	X			X					
Copper, blood	X					X	X		
Pregnancy testing (if applicable)	X								
Edmonton Symptom Assessment System – Revised (ESAS-r) QOL Questionnaire	X		X	X				X	
Brain MRI prior to enrollment	X				X ²			X	
Temozolomide				Concurrent radiation with temozolomide on days 1-42 at 75 mg/m ² . ³ Responding patients will subsequently receive adjuvant TMZ 150 mg/m ² Days 1-5 of each following 28 day cycle ³					
Disulfiram				Days 1-28 of each cycle ⁴					
Copper gluconate				Days 1-28 of each cycle ⁴					
AE assessment			X	X	X	X	X	X	X

1. Follow-up will be as clinically indicated. A chart review will be done at 2 years after the last dose of DSF to look for progression and survival.
2. A confirmatory MRI should be considered in 8 weeks after documentation of complete response (CR) or partial response (PR) if consistent with the institutional standard of care
3. To be taken at bedtime on an empty stomach. Must not be taken within an hour of DSF.
4. To be taken two times a day with meals.
5. AEs will be tracked for 30 days after the last dose of DSF.

10.0 STATISTICAL CONSIDERATIONS

10.1 Definition of Primary Endpoints and Analytical Plan

The co-primary endpoints will be ORR and PFS6. ORR will be defined as the percentage of patients with CR or PR according to the RANO criteria as described in Section 6.0. PFS6 will be defined as proportion of patients that are free from progressive disease (PD) as per RANO criteria or death at 6 months from the date of the first dose of DSF-Cu. PFS6 and median PFS will be estimated using the Kaplan-Meier product-limit method. For unmethylated glioblastoma receiving temozolomide without DSF-Cu, an ORR of less than 10% and PFS6 of less than 20% (Quinn, et al. 2009).

To justify future use of or drug development of DSF-Cu for glioblastoma, we hypothesized that the addition of DSF-Cu to temozolomide would improve ORR to 20% or increase PFS6 to 30%. The sample size is calculated based on the above hypotheses with one-sided exact test at an approximate α level of 0.10 and 80% statistical power. At these type I and II error rates, 14 -20 patients will detect a proportion of patients who have ORR significantly higher than 5% or PFS6 significantly higher than 10%. Of note, previous phase II study testing addition of O⁶-benzylguanine (a MGMT inhibitor) to temozolomide for temozolomide-resistant glioblastoma used similar hypothesis and observed a disappointing ORR of 3% and PFS6 of 9% (Quinn, et al. 2009). This negative phase II study has detailed information on ORR, PFS, and OS as well as associated estimated 95% CIs and will serve as a historical comparison for this study.

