1.5 Sensitizing Glioblastoma to Temozolomide

Currently, temozolomide represents the only systemic therapy that has been shown to improve OS for glioblastoma (Stupp, et al. 2005). A phase II study attempted to re-sensitize recurrent temozolomide-resistant glioblastoma (those who would recur while receiving temozolomide or within 2 months of the last treatment of temozolomide) using an O⁶-methylguanine-DNA methyltransferase (MGMT) inhibitor called O⁶-benzylguanine (OBG) (Quinn, et al. 2009). Since MGMT is an enzyme that repairs DNA damage by alkylating agents such as temozolomide, a MGMT inhibitor is thought to be a rational agent to re-sensitize glioblastoma to temozolomide. Unfortunately, combination of O⁶-benzylguanine and temozolomide did not show any evidence of significant re-sensitization: ORR of 3% (95% CI: 0-15%), PFS6 of 9% (95% CI: 2-21%), and median PFS of 7.5 weeks (95% CI: 4.2-7.9 weeks) (Quinn, et al. 2009).

[figure not shown]

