1.11 Study Rationale

Patients with unmethylated glioblastoma respond poorly to current standard treatment and have a poor prognosis.

Although standard post resection radiation therapy may provide a survival benefit of approximately two months, delayed radiation at or after 8 weeks has been shown to not increase overall survival. This study proposes standard of care treatment with 6 – 6 1/2 weeks of radiation with concurrent temozolomide at 75mgs / m² along with DSF – Cu followed by adjuvant temozolomide at 150mgs / m² for 6 -12 cycles in patients with previously untreated, (aside from surgical resection), unmethylated glioblastoma.

Preclinical studies have identified DSF-Cu as having promising activity in glioblastoma cells and can potentially sensitize temozolomide-resistant cells to temozolomide.

A recent phase I study has demonstrated the feasibility and safety of combining DSF with adjuvant temozolomide in newly diagnosed glioblastoma patients after chemoradiotherapy (Huang, et al. 2016). This clinical trial will evaluate whether the addition of DSF-Cu to temozolomide in patients expected to be temozolomide-resistant can induce anti-tumor responses and validate the potential of DSF-Cu to sensitize glioblastoma to temozolomide.

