3.0 PATIENT SELECTION

Approximately 14-40 patients will be enrolled – depending on the preliminary subset analysis data (when accrual of 14 patients is reached) the study may conclude when 14-20 patient mark is reached.

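### The control rates and historical comparison come from recurrent, temozolomide-resistant disease, but the trial gives first-line chemoradiation, so an inert drug could reject the 10% PFS6 null far more often than 10% of the time

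*Combined protocol and SAP*

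**What the plan says.** Section 10.1 makes ORR and PFS6 co-primary. It gives the control expectation as "For unmethylated glioblastoma receiving temozolomide without DSF-Cu, an ORR of less than 10% and PFS6 of less than 20"%, citing the phase II study of temozolomide plus O6-benzylguanine. The hypothesis is that adding DSF-Cu "would improve ORR to 20% or increase PFS6 to 30"%, and the section ties future use or development of DSF-Cu to that. With a one-sided exact test, alpha of about 0.10 and 80% power, it says 14-20 patients can show "ORR significantly higher than 5% or PFS6 significantly higher than 10"%. It adds that the O6-benzylguanine study "will serve as a historical comparison for this study". Section 3.0 gives a wider enrolment range: "Approximately 14-40 patients will be enrolled".

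Section 1.5 describes the cited study: "A phase II study attempted to re-sensitize recurrent temozolomide-resistant glioblastoma", with ORR 3% and "PFS6 of 9% (95% CI: 2-21%), and median PFS of 7.5 weeks". The present trial excludes any prior radiation or chemotherapy (sections 3.1 and 3.2). It gives 60 Gy with temozolomide and DSF-Cu, then adjuvant temozolomide with DSF-Cu (sections 4.0 and 4.2). The only link between the two settings is the statement in section 1.11 that DSF-Cu is being tested "in patients expected to be temozolomide-resistant".

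**The concern.** In a single-arm trial the null rate is the control group. Here it comes from a different disease stage, and from a regimen described only as temozolomide plus O6-benzylguanine, with no first-line radiation. Section 10.1 labels the rates as unmethylated glioblastoma on temozolomide, which is not how section 1.5 describes the source.

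The protocol's own first-line figures are much better than the benchmark. Median PFS is 5.5 to 7.3 months with adjuvant temozolomide after chemoradiotherapy (section 1.7). At age 70 or older it is 5.3 months with radiation plus temozolomide and 3.9 months with radiation alone (section 1.2). The cited study's median was 7.5 weeks.

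Rejecting PFS6 = 10% might therefore show only that first-line chemoradiation does better than salvage treatment. That result would be read as grounds for developing DSF-Cu.

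**Working it through.** **1. The plan's sample size.** I took the exact binomial test, one-sided alpha at most 0.10 and power at least 80%.

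- PFS6 10% vs 30%: smallest n = 18, reject at 4 or more (alpha 9.8%, power 83.5%).
- ORR 5% vs 20%: smallest n = 21, reject at 3 or more (alpha 8.5%, power 82.1%). At n = 20, power is 79.4%.

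The stated 14-20 is roughly reproduced. At n = 14 with alpha held to 0.10, power is only 64% (PFS6) and 55% (ORR).

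**2. What a 10% null implies.** Under exponential PFS, median = 6 × ln 2 / (−ln 0.10) = 1.8 months. That is below every first-line median in the protocol.

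**3. PFS6 implied by the protocol's medians.** PFS6 = 0.5^((6/median)^k), with Weibull shape k assumed between 0.8 and 2. Example: median 3.9, k = 1 gives 0.5^(1.538) = 34%.

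| Median PFS | k=0.8 | k=1 | k=1.5 | k=2 |
|---|---|---|---|---|
| 3.9 months | 38% | 34% | 27% | 19% |
| 5.3 months | 47% | 46% | 43% | 41% |

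The 5.3-month values are about twice the cited study's upper confidence limit of 21%. I take 25%-46% as the working range for PFS6 without the drug, with 19% as the low extreme.

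**4. Probability that an inert drug rejects PFS6 = 10%.** The plan states no cut-off. Those below are the smallest with exact alpha at most 0.10, assuming 6-month status is known for everyone. Attained alpha is 4.4%, 9.8%, 4.3% and 9.95%.

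Example at n = 14, true PFS6 20%: P(X ≥ 4) = 1 − (0.0440 + 0.1539 + 0.2501 + 0.2501) = 30%.

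| n, cut-off | 19% | 20% | 25% | 34% | 46% |
|---|---|---|---|---|---|
| 14, ≥4 | 27% | 30% | 48% | 76% | 95% |
| 18, ≥4 | 46% | 50% | 69% | 91% | 99% |
| 20, ≥5 | 33% | 37% | 59% | 86% | 98.5% |
| 40, ≥7 | 66% | 71% | 90% | 99% | >99.9% |

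The 20% column uses the plan's own upper figure for control PFS6 and needs no conversion from medians. Rejection reaches 50% once background PFS6 is 25.6% (n=14), 20.0% (n=18), 23.0% (n=20) or 16.5% (n=40).

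**5. Other readings of success.**

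| Rule | 19% | 25% | 34% | 46% |
|---|---|---|---|---|
| Exact test against 20%, n=20, ≥7 | 7% | 21% | 55% | 89% |
| Observed PFS6 ≥30%, n=14, ≥5 | 11% | 26% | 55% | 85% |
| Observed PFS6 ≥30%, n=20, ≥6 | 16% | 38% | 72% | 95% |

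**6. ORR.** The documents give no first-line ORR, so this part cannot be sized. As an illustration only, if true ORR were 10%, the 5% null would be rejected 16% of the time at n = 14 and 32% at n = 20 (cut-off ≥3 in both).

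**The case against.** - **The nulls of 5% and 10% carry no citation.** The reference is attached to the control rates of below 10% and below 20%. This is true. But the tested nulls sit just above the cited study's 3% and 9%, section 10.1 says that study used a similar hypothesis, and it is the named comparison. No other section supplies a first-line null.
- **Unmethylated tumours gain little from temozolomide (section 1.4), so a resistant population is a fair proxy.** This deals with temozolomide but not with radiation. If temozolomide added nothing, the radiation-alone median of 3.9 months is the relevant figure. It comes from patients aged 70 or older, whereas this trial enrols from 18, and it still implies 19%-38%, above the 10% null.
- **The size rests on assumptions.** This stands. The first-line medians are not described as selected by MGMT status or residual tumour, and the start of PFS behind the 5.5-7.3 month figures is not given. The cut-offs are reconstructed, while the plan estimates PFS6 by Kaplan-Meier. At 19% background, the excess is modest under an observed-30% rule and absent against a 20% null.
- **A radiation-plus-temozolomide benchmark may still not match, because section 4.4 allows Optune after radiation.** This is a fair caution for choosing the benchmark. It does not support the present one.
- **The O6-benzylguanine study is a useful precedent as an MGMT inhibitor given with temozolomide.** It can stay as background. Its use as the control is the problem.

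**Conclusion.** The concern holds and must be fixed. The benchmark in section 10.1 describes a different population and treatment from the trial's, and the protocol's own first-line figures contradict a 10% PFS6 null. The stated alpha of about 0.10 fails even at the plan's own 20% figure, where an inert drug rejects 30%-71% of the time across n = 14 to 40. Over the assumed 25%-46% background range, the probability runs from 48% to above 99.9%.

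These sizes depend on the assumed background rate, on derived binomial cut-offs and on complete 6-month follow-up. The mismatch depends on none of them. A positive PFS6 result under the present plan could not separate an effect of DSF-Cu from ordinary first-line chemoradiation. The ORR null has the same source problem, of unknown size.

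**What to change.** In section 10.1, stop using the recurrent-disease study as control source and historical comparison. State a PFS6 null and an ORR null, each with its source, from newly diagnosed, MGMT-unmethylated, incompletely resected patients given radiation plus temozolomide, with PFS timed from the start of treatment. DSF-Cu is to be given concurrently with chemoradiation, so the first-dose clock in section 10.1 and the start-of-treatment clock in section 5.4 should nearly coincide. Set a target above each null, and give n, the minimum number of successes, attained alpha and power.

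Illustration for PFS6, exact alpha at most 0.10:

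| Null | n=20 cut-off (alpha) | Power +20 / +10 points | n=40 cut-off | Power +20 / +10 points |
|---|---|---|---|---|
| 25% | ≥9 (4.1%) | 59% / 24% | ≥15 | 87% / 43% |
| 34% | ≥11 (4.3%) | 56% / 22% | ≥18 | 90% / 51% |
| 46% | ≥13 (6.9%) | 64% / 28% | ≥23 | 90% / 49% |

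If no new null is set, report PFS6 and ORR with confidence intervals beside a first-line benchmark, and remove the statement that reaching ORR 20% or PFS6 30% would justify development.

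The cost is rewording, finding a benchmark and recalculating, with no added procedures. The stated 80% power has to be restated: at n = 20 it becomes 56%-64% for a 20-point gain, against an actual 76% under the present 10% vs 30% rule. Power of 80% for 20 points is first reached at 26-32 patients (31-36 for it to hold at every larger n), inside the 14-40 of section 3.0. A 10-point gain would need roughly 96-128 patients, beyond this trial.

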4.0 TREATMENT PLAN

This study is a single arm, open-label, phase II study of DSF-Cu in combination with concurrent temozolomide and radiation therapy followed by DSF – Cu and adjuvant temozolomide for patients with unmethylated tumors.

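### Section 10.1 claims 80% power for 14–20 patients, but the named exact test gives 55% (ORR) and 64% (PFS6) at 14; the first size giving 80% on both is 21

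*Combined protocol and SAP*

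**What the plan says.** The trial is a single-arm phase II study (section 4.0). Section 10.1 sets two primary endpoints: "The co-primary endpoints will be ORR and PFS6". The hypothesis is that adding DSF-Cu "would improve ORR to 20% or increase PFS6 to 30" per cent. The sample size is said to rest on a "one-sided exact test at an approximate α level of 0.10 and 80% statistical power", and at those error rates "14 -20 patients will detect a proportion of patients who have ORR significantly higher than 5% or PFS6 significantly higher than 10" per cent.

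The section gives no cut-off, no single sample size, and no rule on whether one endpoint or both must succeed. It also puts the background rates without DSF-Cu at "an ORR of less than 10% and PFS6 of less than 20" per cent, and does not say how the tested nulls of 5% and 10% were chosen beside those bounds.

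Section 3.0 says "Approximately 14-40 patients will be enrolled" and that, depending on a preliminary analysis at 14, "the study may conclude when 14-20 patient mark is reached".

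**The concern.** A single-arm exact binomial test with 14 patients has only a few usable cut-offs, and both alpha and power move in large steps between them. Power of 80% across the whole range 14–20, on both endpoints, at alpha near 0.10, therefore looked unlikely.

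The result is meant to justify further development of DSF-Cu. If the study closes at 14, readers will take it as a test with 80% power and 10% alpha. If true power is well below that, a negative result may be over-read as lack of activity. If the cut-off is loosened to recover the power, a positive result carries more false-positive risk than stated.

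**Working it through.** **Inputs (all from section 10.1).** ORR null 5%, alternative 20%. PFS6 null 10%, alternative 30%. One-sided exact test, alpha about 0.10, power 80%. Stated size 14–20.

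**Method.** Let X be the number of successes among n patients. Take the smallest r with P(X ≥ r | null) ≤ 0.10; power is then P(X ≥ r | alternative). This treats every patient as evaluable, including for PFS6 at six months.

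**ORR at n = 14**
- Null 5%: P(0), P(1), P(2) = 0.4877, 0.3593, 0.1229. So P(X ≥ 2) = 0.153 and P(X ≥ 3) = 0.030. The cut-off is 3.
- Alternative 20%: P(0), P(1), P(2) = 0.0440, 0.1539, 0.2501, sum 0.4480. Power = 1 − 0.4480 = **0.552**.

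**PFS6 at n = 14**
- Null 10%: P(0) to P(3) = 0.2288, 0.3559, 0.2570, 0.1142. So P(X ≥ 3) = 0.158 and P(X ≥ 4) = 0.044. The cut-off is 4.
- Alternative 30%: P(0) to P(3) = 0.0068, 0.0407, 0.1134, 0.1943, sum 0.3552. Power = 1 − 0.3552 = **0.645**.

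**Across the range, alpha ≤ 0.10**

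| n | ORR cut-off | alpha | power | PFS6 cut-off | alpha | power |
|---|---|---|---|---|---|---|
| 14 | ≥3 | 0.030 | 0.552 | ≥4 | 0.044 | 0.645 |
| 15 | ≥3 | 0.036 | 0.602 | ≥4 | 0.056 | 0.703 |
| 16 | ≥3 | 0.043 | 0.648 | ≥4 | 0.068 | 0.754 |
| 17 | ≥3 | 0.050 | 0.690 | ≥4 | 0.083 | 0.798 |
| 18 | ≥3 | 0.058 | 0.729 | ≥4 | 0.098 | 0.835 |
| 19 | ≥3 | 0.067 | 0.763 | ≥5 | 0.035 | 0.718 |
| 20 | ≥3 | 0.075 | 0.794 | ≥5 | 0.043 | 0.762 |
| 21 | ≥3 | 0.085 | 0.821 | ≥5 | 0.052 | 0.802 |
| 40 | ≥5 | 0.048 | 0.924 | ≥7 | 0.100 | 0.976 |

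Within 14–20, PFS6 passes 80% only at 18, and ORR peaks at 79.4% at 20. The first size with 80% on both is 21. Power does not rise steadily after that: 22 also works (0.846 and 0.836), but at 23–26 the ORR cut-off moves to 4 and ORR power falls to 0.703–0.793. Both endpoints are above 80% again from 27.

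**Looser cut-offs at n = 14.** ORR ≥2 gives alpha 0.153 and power 0.802. PFS6 ≥3 gives alpha 0.158 and power 0.839.

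**Could a normal approximation explain the range?** With n = [z₀.₉₀√(p₀q₀) + z₀.₈₀√(p₁q₁)]² / (p₁ − p₀)²:
- ORR: (1.2816 × 0.2179 + 0.8416 × 0.4)² / 0.0225 = 16.9, so 17.
- PFS6: (1.2816 × 0.3 + 0.8416 × 0.4583)² / 0.04 = 14.8, so 15.

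An arcsine approximation gives 20 and 17. These lie inside 14–20, but they are not the exact test the plan names, and none of them supports 14.

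**Success rule at n = 14, if the endpoints were independent (an assumption)**
- Either suffices, both alternatives true: 1 − 0.448 × 0.355 = 0.841.
- Either suffices, only the ORR alternative true: 1 − 0.448 × (1 − 0.044) = 0.572.
- Either suffices, only the PFS6 alternative true: 1 − (1 − 0.030) × 0.355 = 0.656.
- Both required: 0.552 × 0.645 = 0.356. Whatever the dependence, it cannot exceed 0.552.

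**The case against.** The plan gives a range, and its upper end is nearly right: at 20, ORR power is 79.4%, which most would call 80%. The word *approximate* before alpha also allows some slack. At 20, a PFS6 cut-off of 4 gives power 0.893 at alpha 0.133; at 19 it gives 0.867 at alpha 0.115. Fourteen is also the point of a preliminary analysis, and enrolment may reach 40, where power is 92% and 98%. The plan says *or*, and under an either-endpoint rule 14 patients could reach 84%.

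The point about the upper end stands: the shortfall there is small and depends on how strictly 0.10 is read. The rest does not rescue the lower end. At 14, 80% power needs alpha of 0.153 or more, over half again the stated level. Section 3.0 lets the study conclude at 14–20, and section 10.1 attaches the 80% claim to exactly that range. The 84% needs both alternatives true and independent endpoints; with non-negative dependence it lies between 64% and 84%, and no either-endpoint rule is stated.

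The nulls are a lesser matter. Rates of 5% and 10% do not contradict background rates described only as below 10% and 20%, and the historical study quoted in section 10.1 had 3% and 9%. They need a sentence of justification. As a sensitivity case only, nulls of 10% and 20% would give power of 30% (ORR) and 22% (PFS6) at 14.

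**Conclusion.** The power statement is wrong as written. On the plan's own nulls, targets and test, 14 patients give 55% power for ORR and 64% for PFS6, so type II error is 45% and 36% rather than 20%. Sizes 15 and 16 also fall short on both endpoints (60% and 70%; 65% and 75%). No size in 14–20 reaches 80% on both with alpha at or below 0.10, although 20 comes near. At 40 the claim would hold comfortably.

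The figures treat each endpoint separately, assume a single analysis, and assume every patient can be classified at six months. Section 10.1 plans Kaplan–Meier estimation of PFS6 and gives no dropout rate; losses would lower power further.

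**What to change.** In section 10.1:

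- State one null and one alternative per endpoint, with the reason for each null.
- Say whether success needs either endpoint or both. If either suffices, also give the overall alpha, which is at most the sum of the two: 0.074 at 14, 0.119 at 20 and 0.137 at 21.
- For the chosen size, or each permitted stopping size, give the integer cut-off, exact alpha and exact power. Remove the claim of 80% power at 14.

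Three ways to complete this with the present rates:
- **Allow closure at 14:** state 55% (ORR ≥3) and 64% (PFS6 ≥4).
- **Keep 20:** state ORR ≥3, alpha 0.075, power 0.79; PFS6 ≥5, alpha 0.043, power 0.76.
- **Use 21:** ORR ≥3, alpha 0.085, power 0.82; PFS6 ≥5, alpha 0.052, power 0.80. This meets the stated specification per endpoint, but one unevaluable patient takes PFS6 back below 80%. Other sizes above 21 must be checked individually because of the dip at 23–26.

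If success can be declared at the 14-patient analysis as well as at the end, error rates must be given for the two looks together. For PFS6, success at ≥4 of 14 or ≥5 of 21 has alpha 0.069 rather than 0.052. Stopping at 14 for lack of activity would reduce power.

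Add a cross-reference in section 3.0. The cost is wording and a less favourable stated power at 14. No patients need be added; 21 is one above the 14–20 range and within the planned 14–40.
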